2.13 Interim analysis

After all participants complete their baseline visit, the demographic and baseline characteristics may be summarized to help design new studies. No analysis will be performed using post-baseline data. Thus, there is no need to adjust the level of significance for such interim analysis of baseline data.

3 Sample size calculation

The sample size was calculated for the two primary efficacy variables with adjustment for multiple testing by using the Bonferroni procedure.

For primary efficacy variable 1, i.e., percent change from baseline in LDL-C, the standard deviation is assumed to be 40, partly based on the results from ORION-10 and ORION-11 clinical trials and considering that the standard deviation will likely be larger in this trial since changes in lipid-lowering therapy are allowed in both treatment groups. An expected mean treatment difference of 15 is assumed, which is smaller than the mean difference observed in the Phase III trials, to account for 1) potential lower utilization of background lipid-lowering therapy in the inclisiran + usual care treatment group compared to the usual care treatment group, and 2) the ability to add non-statin lipid lowering therapy in the usual care treatment group. A z-test, an allocation ratio of 1:1, and a two-sided significance level of 0.025 were also used in the calculation of sample size.

[Table 3-1](#) considers total sample sizes for expected mean treatment differences of 10, 15, and 20, and powers of 0.85 and 0.90 (nQuery Version 8.4.1.0). From [Table 3-1](#), an expected mean treatment difference of 15 (based on means of 40 and 55 at Day 330 in the usual care and inclisiran + usual care treatment groups, respectively) and a power of 0.85 were chosen to provide a total sample size of 306 participants.

Table 3-1 Sample Size Calculations for Percent Change from Baseline in LDL-C

Mean treatment difference	Power = 0.85	Power = 0.90
10	688	796
15	306	354
20	172	200

For primary efficacy variable 2, i.e., achieving LDL-C < 70 mg/dL (yes, no), a z-test, an allocation ratio of 1:1, and a two-sided significance level of 0.025 were used in the calculation of sample size.

[Table 3-2](#) considers total sample sizes for several expected proportions of participants who achieve LDL-C < 70 mg/dL at Day 330 in the usual care and inclisiran + usual care treatment groups, and powers of 0.85 and 0.90 (nQuery Version 8.4.1.0). From [Table 3-2](#), the expected proportions of 0.55 and 0.75 in the usual care and inclisiran + usual care treatment groups, respectively, and a power of 0.85 were chosen to provide a total sample size of 242 participants.

Table 3-2 Sample Size Calculations for Achieving LDL-C < 70 mg/dL

Proportion in usual care group	Proportion in inclisiran + usual care group	Power = 0.85	Power = 0.90
0.50	0.65	464	536
0.50	0.70	256	294
0.55	0.70	446	514
0.55	0.75	242	278

Based on the sample size calculations in the tables above, a total sample size of 306 together with a loss to follow-up rate of 20% at Day 330 require approximately 384 participants (192 participants per treatment group) to be randomized. This will also allow examination of subgroups with reasonable sample sizes.

4 Change to protocol specified analyses

Change from Protocol version 04 (amended protocol) include the following:

1. Protocol Section 12.4.2 states that an unstructured working correlation matrix will be assumed for the MMRM. An unstructured covariance matrix will be used instead. In case of convergence issues, compound symmetry will be tried instead.
2. The protocol uses Day 0 as the first inclisiran dose day. In order to aid in counting of dosing days the first dose day will be referred to as Day 1.
3. Protocol Section 12 notes that the interquartile range will be provided. In order to streamline the tables this statistic was removed.
4. Protocol Section 12.2 notes that relevant medical histories and current medical conditions at baseline would be summarized using the Safety Set, the FAS was used instead.
5. Protocol Section 12.5.1 lists out secondary efficacy variables. The analysis of variable #21 (Intensity of lipid-lowering therapy (decrease in dose, no change in dose, increase in dose) was modified slightly. Intensity of therapy is only available for statins, not for other lipid-lowering therapies used in this study. Therefore, for each participant and analysis visit, the highest statin intensity on each nominal visit date will be compared to baseline statin intensity.
6. Protocol Section 12.5.2 notes that all vital signs and all laboratory data will be listed. In order to streamline the listings, only abnormal vital signs and laboratory data will be provided.
7. Use of prohibited medication as defined in Protocol Section 6.2.2 (monoclonal antibodies directed against PCSK9) will be considered as an intercurrent event for participants in the inclisiran + usual care group and was therefore incorporated to all estimands as applicable.

5 Appendix

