Clinical Development

KJX839

CKJX839A1US01 / NCT04873934

A randomized, controlled, multicenter, open-label trial comparing a hospital post-discharge care pathway involving aggressive LDL-C management that includes inclisiran with usual care versus usual care alone in patients with a recent acute coronary syndrome (VICTORION-INCEPTION)

Statistical Analysis Plan (SAP)

Document type: SAP Documentation

Document status: Final Amendment 01

Release date: 29-Aug-2024

Number of pages: 45

Property of Novartis
Confidential

May not be used, divulged, published or otherwise disclosed
without the consent of Novartis

Template Version 6.0, Effective from 23-Nov-2022

Document History – Changes compared to previous final version of SAP

Date, Version	Time point	Reason for update	Outcome for update	Section and title impacted (Current)
16-Jun-2021, Final v1.0	Prior to DB lock	Creation of final version	N/A - First version	NA
29-Aug-2024, Final Amendment 01	Prior to DB lock	Necessary correction or clarification; harmonization across inclisiran studies	Clarification on use of calculated LDL-C for statistical analysis and use of SI and/or US conventional units for selected lab parameters. Definition of screening value Subgroups for subgroup analyses of primary efficacy variables added and updated. List of demographic variables updated. Definition of changes in lipid-lowering therapies prior to baseline was added. Methodology in case of non-convergence of statistical models was added. Sensitivity analyses were added to address participants with low baseline LDL-C. Common adverse event tables using 3% within either treatment group as the threshold was added. Addition of adverse events of special interest terms. Reference and definition of eGFR derivation were added. Summary tables for new onset or worsening of diabetes were added. Update of baseline diabetes status to baseline glycemic status. Summary tables for participants satisfying Hy's Law will be repeated excluding the normal baseline value requirement.	Section 2.1 Section 2.1.1 Section 2.2.1 Section 2.3.2 Section 2.4.2 Section 2.5.2 Section 2.5.5 Section 2.7.1 Section 2.7.1.1 Section 2.7.3 Section 2.7.3
				[REDACTED]
				[REDACTED]

Date, Version	Time point	Reason for update	Outcome for update	Section and title impacted (Current)
			Added time to event analyses for composite MACE and individual components. [REDACTED]	Section 2.12 [REDACTED]

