2.1 Data analysis general information

It is planned that the data from all centers that participate in this protocol will be combined, so that an adequate number of participants will be available for analysis.

Any data analysis carried out independently by the investigator should be submitted to Novartis before publication or presentation.

The analysis will be performed at the end of the trial, after the clinical database is locked.

Unless otherwise specified, all statistical tests will be conducted against a two-sided alternative hypothesis, employing a significance level of 0.05.

Efficacy, safety, and other data will be summarized. For continuous variables, summary statistics (mean, standard deviation, median, 25th and 75th percentiles, minimum, and maximum) at each time point and for change from baseline to each time point will be reported by treatment group. For discrete variables, frequency counts and percentages at each time point will be reported by treatment group.

LDL-C values, lipid parameters, and laboratory units

Any statistical analysis involving LDL-C will be based on calculated LDL-C values as provided by the central laboratory. For the remainder of this SAP and the corresponding output shells, the abbreviated term “LDL-C” refers to calculated LDL-C.

Tabular summaries, listings, and figures of lipid parameters, creatinine, and fasting glucose will be provided in US conventional units. Select analyses of these parameters will be provided in SI units as well. All other laboratory parameters will be reported in SI units. Both US conventional and SI units will be included in SDTM and ADaM datasets as applicable per laboratory parameter. The lipid parameters include the following, with US and SI units as applicable in this study:

1. LDL Cholesterol (mg/dL, mmol/L)
2. Total Cholesterol (mg/dL, mmol/L)
3. HDL Cholesterol (mg/dL, mmol/L)
4. Non-HDL Cholesterol (mg/dL, mmol/L)
5. VLDL Cholesterol (mg/dL, mmol/L)
6. Triglycerides (mg/dL, mmol/L)
7. Apolipoprotein B (mg/dL)

8. Lipoprotein(a) (nmol/L)

Due to differences in measurement techniques as well as molecular differences between individuals, a standardized conversion factor is not available to convert Lipoprotein(a) values from standard to US conventional units. Therefore, Lipoprotein(a) results will only be reported in nmol/L.

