2.5.2 Statistical hypothesis, model, and method of analysis

Primary efficacy variable 1

The null hypothesis is that the mean percent change from baseline in LDL-C at Day 330 for inclisiran + usual care and usual care treatment groups are equal. The alternative hypothesis is that the mean percent change from baseline in LDL-C at Day 330 for inclisiran + usual care treatment group is not equal to that of the usual care treatment group.

Primary efficacy variable 1 will be analyzed using mixed-effects model repeated measures (MMRM) with treatment, visit (Day 90, Day 270, Day 330), baseline, treatment-by-visit interaction, and baseline-by-visit interaction as explanatory variables. An unstructured covariance matrix will be assumed for this model. Least-squares mean of each treatment group, least-squares mean treatment difference, two-sided 97.5% confidence intervals for the treatments, two-sided 97.5% confidence interval for the treatment difference, and p-value based on the fitted MMRM will be reported for each applicable visit (day). If the p-value based on a two-sided test for treatment at Day 330 is < 0.025 and the corresponding least squares mean treatment difference ([inclisiran + usual care] - usual care) is less than 0, statistical significance in favor of inclisiran + usual care is shown. All efforts will be made to follow up participants until the end of the study. Participants will be expected to follow the visit schedule and assessments even after discontinuation of study treatment. Data after participants discontinued study treatment will be used in the analysis ("retrieved dropout"). In case of non-convergence of a model while using an unstructured covariance matrix, compound symmetry will be tried instead.

The primary analysis of primary efficacy variable 1 will be based on the FAS. The primary analysis of this variable will be repeated for the Per-Protocol Set, Restricted Set 1, and Restricted Set 2.

Primary efficacy variable 2

Let π_j denote the probability of achieving LDL-C < 70 mg/dL at Day 330 for treatment group j , $j = 0, 1$, where 0 corresponds to usual care and 1 corresponds to inclisiran + usual care. Accordingly, $\pi_j/(1 - \pi_j)$ is the odds for treatment group j , $j = 0, 1$.

The following null hypothesis (H_0) will be tested against the alternative hypotheses (H_A), corresponding to the comparison inclisiran + usual care versus usual care:

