$$H_0: [\pi_1/(1 - \pi_1)]/[\pi_0/(1 - \pi_0)] \leq 1 \text{ versus } H_A: [\pi_1/(1 - \pi_1)]/[\pi_0/(1 - \pi_0)] > 1$$

Primary efficacy variable 2 will be analyzed at each post-baseline visit using a logistic regression model with treatment and baseline LDL-C as explanatory variables (Stokes et al. 2012). The odds ratio, two-sided 97.5% confidence interval for the odds ratio, and p-value based on the fitted model will be reported. If the p-value based on a two-sided test for inclisiran + usual care versus usual care at Day 330 is < 0.025 and the corresponding odds ratio is greater than 1, statistical significance in favor of inclisiran + usual care is shown. In case of non-

convergence of a logistic regression model, the model will be updated to use Firth's penalized likelihood method (Firth 1993). If the model using Firth's method still shows convergence issues then the baseline LDL-C covariate may be removed from the model. Two-sided 97.5% confidence intervals for the proportion of participants who achieve LDL-C < 70 mg/dL in each treatment group will be calculated, using the normal approximation to the binomial distribution.

The primary analysis of primary efficacy variable 2 will be based on the FAS. The primary analysis of this variable will be repeated for the Per-Protocol Set, Restricted Set 1, and Restricted Set 2.

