2.5.4 Handling of missing values not related to intercurrent event

For the primary analysis of primary efficacy variable 1, the MMRM implicitly imputes missing data under a missing at random assumption.

For the primary analysis of primary efficacy variable 2, participants with missing LDL-C data will be assumed to have LDL-C \geq 70 mg/dL (i.e., “non-responder”).

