2.5.6 Supplementary analyses

A supplementary analysis of primary efficacy variable 1 will be based on the following estimand:

- Population: Defined through appropriate inclusion/exclusion criteria to reflect the targeted population
- Variable: Percent change from baseline in LDL-C [The primary analysis time point is at Day 330.]

- Treatment: Inclisiran + usual care or usual care
- Remaining intercurrent events: 1. Potential use of inclisiran by participants in the usual care group. 2. Discontinuation of study treatment. 3. Use of prohibited medication (monoclonal antibodies directed against PCSK9, as defined in [Table 2-3](#)) in the inclisiran + usual care group. Data after the occurrence of either one of the above three intercurrent events will be excluded from the analysis (using MMRM).
- Summary measure: Least-squares mean difference between inclisiran + usual care group and usual care group

A supplementary analysis of primary efficacy variable 2 will be conducted by repeating the primary analysis based on observed LDL-C values per visit. Missing data will not be imputed. Therefore, the denominator for deriving the proportion of participants achieving LDL-C <70 mg/dL will be the number of participants with non-missing LDL-C per visit and treatment group.

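### Bonferroni on the two primary variables is valid and matches the sample size, but Holm keeps the same two-sided 0.05 family-wise error and would add about 5 to 8 points to the power to claim both in the sized case (optional change)

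*SAP*

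**What the plan says.** The two primary variables are percent change from baseline in LDL-C (variable 1) and achieving LDL-C < 70 mg/dL (variable 2), both at Day 330.

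- **Overall level.** SAP 2.1 states that, unless otherwise specified, "all statistical tests will be conducted against a two-sided alternative hypothesis, employing a significance level of 0.05".
- **Multiplicity.** SAP section 3 and protocol 12.8.1 describe "adjustment for multiple testing by using the Bonferroni procedure", with a two-sided 0.025 in each sample size calculation.
- **Decision rule, variable 1** (SAP 2.5.2, protocol 12.4.2): "If the p-value based on a two-sided test for treatment at Day 330 is < 0.025" and the difference favours inclisiran, success is declared.
- **Decision rule, variable 2** (same sections): "If the p-value based on a two-sided test for inclisiran + usual care versus usual care at Day 330 is < 0.025" and the odds ratio exceeds 1, success is declared.
- **Sample size.** SAP section 3 takes "a total sample size of 306 together with a loss to follow-up rate of 20% at Day 330" to reach 384 randomized, 192 per arm.
- **Missing data, variable 2.** Under SAP 2.5.4, "participants with missing LDL-C data will be assumed to have LDL-C" at or above 70 mg/dL. SAP 2.5.6 adds a supplementary analysis, "repeating the primary analysis based on observed LDL-C values per visit".

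Neither document has a step-down rule or passes alpha from one variable to the other.

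**The concern.** The two 0.025 thresholds use up the 0.05 only while both null hypotheses are still in play. Once one has been rejected, at most one true null remains, and testing it at 0.05 keeps the family-wise error at 0.05. The plan holds the second test at 0.025 anyway. With Day 330 p-values of 0.001 and 0.03, both in the right direction, the plan claims one primary variable and Holm would claim both.

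What is at stake is the second claim only. Protocol 2.1 and SAP 1.2.1 justify the estimand by the effect on both variables, but no passage requires both to succeed, and the chance of winning at least one is identical under the two rules. This is unused power, not an error.

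**Working it through.** **Inputs.** From SAP section 3: difference 15, SD 40, proportions 0.55 v 0.75, two-sided 0.025 each, power 0.85, 1:1 allocation, 20% loss. The correlation between the two test statistics is not in the documents; 0 to 0.9 is assumed. Critical values are 2.241 (two-sided 0.025) and 1.960 (two-sided 0.05); the normal quantile for 0.85 power is 1.036.

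**Reproducing the plan's sample size.**
- Variable 1: 2 × (2.241 + 1.036)² × 40² / 15² = 152.8, so 153 per arm and 306 in total.
- Variable 2, variance pooled under the null (mean proportion 0.65): (2.241 × √0.455 + 1.036 × √0.435)² / 0.20² = 120.5, so 121 per arm and 242 in total.
- Loss: 153 / 0.8 = 191.25, so 192 per arm and 384 in total.

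All cells of Tables 3-1 and 3-2 reproduce the same way.

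**Power of each variable at 0.025.**
- Variable 1, 153 per arm: 15 / (40 × √(2/153)) = 3.280; 3.280 − 2.241 = 1.039, power 0.850. At 192 per arm, 0.924.
- Variable 2, 153 per arm: (√153 × 0.20 − 2.241 × √0.455) / √0.435 = 1.459, power 0.928. At 192 per arm, 0.972.
- Variable 2 with 20% missing in each arm counted as failure: 0.8 × 0.55 = 0.44 and 0.8 × 0.75 = 0.60 on 192 per arm, power 0.818.

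**Power to claim both.** With Z1 and Z2 bivariate normal and positive in the favourable direction:
- Bonferroni: P(Z1 > 2.241, Z2 > 2.241).
- Holm: P(Z1 > 2.241, Z2 > 1.960) + P(Z1 > 1.960, Z2 > 2.241) − P(Z1 > 2.241, Z2 > 2.241).

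Sized case at correlation 0.6: 0.835 + 0.864 − 0.818 = 0.881, against 0.818 under Bonferroni.

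| Case (difference 15) | Correlation 0 | 0.6 | 0.9 | Gain, points |
|---|---|---|---|---|
| 20% loss, 153 evaluable per arm for both | 0.789 to 0.868 | 0.818 to 0.881 | 0.843 to 0.895 | 7.9, 6.4, 5.2 |
| 20% loss, missing counted as failure for variable 2 | 0.696 to 0.797 | 0.745 to 0.824 | 0.788 to 0.847 | 10.2, 7.9, 5.9 |
| No loss, 192 per arm | 0.898 to 0.943 | 0.909 to 0.947 | 0.921 to 0.952 | 4.5, 3.7, 3.1 |

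Each cell runs from Bonferroni to Holm; gains were taken before rounding. At correlation 0.6 in the sized case, power for variable 1 alone rises from 0.850 to 0.897 and for variable 2 from 0.928 to 0.945. The chance of at least one success there is 0.960 under either rule.

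**Larger effects** (gain in points over correlations 0 to 0.9).

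| True effects | 153 evaluable | Missing as failure | No loss |
|---|---|---|---|
| Difference 20, variable 2 still 0.55 v 0.75 | 3.1–3.9 | 6.5–7.2 | 1.4–1.6 |
| Difference 20, 0.55 v 0.80 (assumed) | 0.8–1.2 | 1.9–2.8 | 0.2–0.3 |

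**Error rate.** If both nulls are true, Holm makes an error only when the smaller p-value is below 0.025, exactly as Bonferroni does: 0.0494, 0.0450 and 0.0362 at correlations 0, 0.6 and 0.9. If one null is true, an error needs that variable's p-value below 0.05, so the rate is at most 0.05.

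**The case against.** **There is no defect.** Levels, decision rules and sample size agree, no objective needs both variables, and no secondary hierarchy depends on a second primary win. This stands, and is why the point is optional.

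**Bonferroni gives matching intervals.** The planned 97.5% intervals agree with the 0.025 tests. Under Holm, the variable tested second can be declared significant while its 97.5% interval includes no effect, in exactly the trials where Holm gains. This is a real cost, and preferring matching intervals is a legitimate choice.

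**The headline gain rests on a cautious effect.** SAP section 3 says 15 is below the difference seen in Phase III. With larger effects on both variables the gain nearly vanishes, as the second table shows. This stands.

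**The calculation is not the planned model.** These are z-tests without baseline adjustment, whereas the MMRM adjusts for baseline and uses earlier visits. If that lowered the effective SD to 36 (an assumption), the 153-per-arm gain would be 3.5 to 6.1 points. Against this, the non-responder rule for variable 2 pushes the gain up, to 5.9 to 10.2 points at SD 40.

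**The ends of the correlation range are unlikely.** Both variables come from the same Day 330 LDL-C, so 0 is implausible. A normal variable correlates at most √(2/π) = 0.80 with its own split into two classes, so 0.9 looks high. Between 0.6 and 0.8 the sized-case gain is 6.4 to 5.6 points, inside the stated range.

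**It is late.** Treatment is open-label, and the SAP amendment of 29 August 2024 is final. Relaxing a primary threshold now invites suspicion, and the change may be moot. The SAP history marks that amendment "Prior to DB lock", and the documents do not say whether lock has followed. This limits when the change is acceptable; it does not alter the method point.

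**Conclusion.** The point holds as an optional improvement. Under the plan's own sizing assumptions, fixed 0.025 tests give up 5.2 to 7.9 points of power to claim both primary variables on 153 evaluable per arm, 5.9 to 10.2 points if 20% are lost and counted as failures for variable 2, and 3.1 to 4.5 points with no loss. These figures rest on an assumed correlation of 0 to 0.9, unadjusted z-tests, equal loss in the two arms, and effects of 15 and 0.55 v 0.75. The current plan remains valid, and a sponsor that does not need both claims, or that values intervals matching each test, loses nothing by keeping it.

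**What to change.** Only if the database is not locked and those deciding have not seen by-arm LDL-C results:

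1. In SAP 2.5.2, compare the smaller Day 330 p-value with 0.025 and, if it is significant, the other with 0.05. Keep both direction conditions.
2. Record the change in SAP section 4, with a dated statement that by-arm results had not been seen.
3. Align protocol 12.4.2 and the protocol summary by amendment, and state whether the 0.025 threshold for the z-test in protocol 12.4.5 stays.
4. Keep the 97.5% intervals, noting that the interval for the variable tested second may include no effect when Holm rejects.

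If lock has occurred or by-arm results are known, keep Bonferroni.

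**Cost.** No new data or participants, and the sample size is unchanged. The price is a written amendment with the approvals in protocol 14.1 (sponsor, ethics boards, and health authorities where required) across up to about 130 sites, a possible mismatch between test and interval for the second variable, and some loss of credibility from relaxing a threshold late in an open-label trial.
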